10.2.2. Day 5 Visit

This visit will be performed for safety purposes. Patients will be instructed that they must take the Day 5 study drug dose at the clinic before 12:00 pm (noon), after the Holter monitor has been placed. The following assessments will be performed at the Day 5 visit for the first 75 randomized patients:

- Observation of patients predose and for the first 6 hours following dose administration, including hourly vital sign monitoring
- ECG predose and at Hour 6
- Continuous Holter monitoring 15 minutes predose and for 24 hours following dose administration

If clinically significant cardiac conduction abnormalities are not observed in the first 75 patients that are treated, Day 5 monitoring will be discontinued for the remaining patients enrolled in the study. After that time, the first-dose monitoring strategy should be repeated at Day 5 if any

cardiac safety issues were observed at Day 1. If any safety issues are identified during Day 5 monitoring, then the monitoring guidelines in [Section 10.2.1.1](#) should be followed.

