- Day 1 (all Part A patients): Observation of patients predose and for the first 6 hours following initial dose administration; ECG predose and at Hour 6; continuous Holter monitoring for 15 minutes predose and for 24 hours following dose administration.
- Day 5 (first 75 patients): Observation of patients predose and for the first 6 hours following dose administration; ECG predose and at Hour 6; continuous Holter monitoring for 15 minutes predose and for 24 hours following dose administration.
- Day 8 (first 75 patients): Continuous Holter monitoring for 15 minutes predose and for 24 hours following dose administration.

If clinically significant heart rate reductions or cardiac conduction abnormalities are not observed in the first 75 patients that are treated, Day 5 and Day 8 monitoring will be discontinued for the remaining patients enrolled in the study.

Part B

Monitoring during initial dosing for Part B will include:

Day 1 (all Part B patients): Observation of patients predose and for the first 6 hours following initial dose administration; ECG predose and at Hour 6

Monitoring during initial dosing for Part B may be modified based on safety and tolerability results observed during Part A, and will be implemented as needed in an amendment to this clinical study protocol.

Part A and Part B

Safety and tolerability will be evaluated in this study by the incidence and type of AEs, serious adverse events (SAEs), AEs leading to discontinuation of study treatment, the incidence and type of laboratory abnormalities, vital sign, ECG, and physical exam abnormalities in all patients. In addition, descriptive characterization of target AEs of interest including bradycardia and heart conduction abnormalities (ECG; continuous Holter monitoring [Part A only]), pulmonary toxicity (FEV₁, FVC, and lung diffusion capacity testing [DLCO] measurements), macular edema (ophthalmic exams), hepatotoxicity (LFTs), cutaneous malignancy (dermatological exams), and suicidality (Columbia- Suicide Severity Rating Scale [C-SSRS])

will occur in both Part A and Part B of the study.

PK and PD Endpoints:

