Target AEs of interest in study RPCS 001 were closely monitored and included bradycardia and other heart conduction abnormalities, pulmonary toxicity, hepatotoxicity, macular edema, and suicidal ideation. No AEs were reported for LFT elevation, macular edema, or suicidal ideation. Two subjects who received 2 mg RPC1063 for 7 days had Grade 1 pulmonary-related adverse events of obstructive airways disorder. For the two subjects, forced vital capacity (FVC) and forced expiratory volume at 1 second (FEV₁) declined to >20% below their baseline values on Day 7 (last dosing day) and Day 14 (last post-dose follow-up visit). Subjects were followed and values returned to baseline off therapy.

Four subjects had Grade 2 cardiac-related AEs of bradycardia and/or conduction abnormality. One subject experienced a Grade 2 second degree AV block and associated nausea after receiving a single dose of 1.5 mg RPC1063 that led to study discontinuation. At a dose of 3 mg RPC1063, 2 subjects reported AEs of Grade 2 sinus arrest, and 1 subject reported an AE of sinus bradycardia. These events resolved within 24 hours with no medical intervention.

All subjects, including those administered placebo, showed an initial reduction in HR following dosing on Day 1. Subjects who received RPC1063 had a greater decrease in HR compared to placebo subjects, and there was evidence of a dose-dependent decrease in absolute heart rate. Lower doses of RPC1063 led to less change in absolute heart rate over time, with the greatest change from baseline during the first 12 hours following treatment of -5.2 bpm and -13.2 bpm for doses of 0.3 mg and 1 mg, respectively. In general, most of the decrease in HR was observed within the first 6 hours after study drug was administered.

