8.2.2. Safety (Secondary) Endpoints

Part A

Cardiac safety and tolerability during initial dose titration will be evaluated in Part A patients according to the following monitoring schedule:

- Day 1 (all Part A patients): Observation of patients predose and for the first 6 hours following initial dose administration; ECG predose and at Hour 6; continuous Holter monitoring for 15 minutes predose and for 24 hours following dose administration.
- Day 5 (first 75 patients): Observation of patients predose and for the first 6 hours following dose administration; ECG predose and at Hour 6; continuous Holter monitoring for 15 minutes predose and for 24 hours following dose administration.

- Day 8 (first 75 patients): Continuous Holter monitoring for 15 minutes pre-dose and for 24 hours following dose administration.

If clinically significant heart rate reduction or cardiac conduction abnormalities are not observed in the first 75 patients that are treated, Day 5 and Day 8 monitoring will be discontinued for the remaining patients enrolled in the study.

Part B

Monitoring during initial dosing for Part B will include:

Day 1 (all Part B patients): Observation of patients pre-dose and for the first 6 hours following initial dose administration; ECG pre-dose and at Hour 6

Monitoring during initial dosing for Part B may be modified based on safety and tolerability results observed during Part A, and will be implemented as needed in an amendment to this clinical study protocol.

Part A and Part B

Safety and tolerability will be evaluated in this study by the incidence and type of AEs, SAEs, AEs leading to discontinuation of study treatment, the incidence and type of laboratory abnormalities, vital sign, ECG, and physical exam abnormalities in all patients. In addition, descriptive characterization of target AEs of interest including bradycardia and heart conduction abnormalities (ECG, vital signs, continuous Holter monitoring [Part A only]), pulmonary toxicity (FEV₁, FVC measurements), and lung diffusion capacity testing [DLCO measurements), macular edema (optical coherence tomography [OCT]), hepatotoxicity (LFTs), cutaneous malignancy (dermatological exams), and suicidality (Columbia- Suicide Severity Rating Scale [C-SSRS]) will occur in both Part A and Part B of the study.

Safety assessments will include the following:

- AEs
- Laboratory evaluations
- Vital sign measurements
- ECG results
- Continuous Holter monitoring

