TSH = Thyroid stimulating hormone, RPR = rapid plasma reagin; TB = tuberculosis, ECG = electrocardiogram, IVRS = interactive voice response system, MRI = magnetic resonance imaging, EDSS = Expanded Disability Status Scale, MSFC = Multiple Sclerosis Functional Composite, LCLA = low-contrast letter acuity test; MSQOL = Multiple sclerosis quality of life, OCT = optical coherence tomography, C-SSRS = Columbia- Suicide Severity Rating Scale, PK = pharmacokinetics, AE/SAE = adverse events/serious AE

Footnotes to Table 1

- 1 If clinically significant heart rate reductions or cardiac conduction abnormalities are not observed in the first 75 patients that are treated, Day 5 and Day 8 monitoring will be discontinued for the remaining patients enrolled in the study.
- 2 Week 24 visit is the End of Treatment visit of the double-blind placebo-controlled period.
- 3 At Day 1 an interim medical history will be performed to complete the screening medical history. Medical events that occur between screening and first dose will be recorded as medical history. All SAEs must be reported from the time of signing the informed consent; AEs are collected after the first dose.
- 4 Laboratory tests include Hematology and Chemistry. Urinalysis is only performed at Screening and Week 24 only.
- 5 Serum beta human chorionic gonadotrophin (hCG) at screening, urine beta hCG at each visit. If the urine pregnancy test is positive, do not dose and confirm with a serum pregnancy test.
- 6 Serology testing will be performed at screening to determine the patient's immune status with respect to the following viruses: Human immunodeficiency virus (HIV) antibodies, anti-hepatitis A virus IgM, hepatitis B surface antigen (HBsAg) and anti-hepatitis B core antigen (HBcAg) IgM, anti-hepatitis C virus (HCV) IgG or IgM. In addition, patients must have documentation of positive Varicella Zoster Virus (VZV) IgG antibody status or complete VZV vaccination at least 30 days prior to first dose of study medication.
- 7 The TB screening (purified protein derivative) should be performed during the screening period and all testing must be completed prior to administration of study drug on Day 1. As available locally, an interferon gamma release assay such as QuantIFERON Gold test may be used as an alternative screening TB test, or as a confirmatory test to rule out a false positive result using purified protein derivative.
- 8 Height at screening only.

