Additional extended monitoring should be instituted until the finding has resolved in the following situations:

- The heart rate 6 hours post-dose is < 45 bpm
- The heart rate 6 hours post-dose is at the lowest value post-dose (suggesting that the maximum PD effect on the heart may not have occurred)
- The ECG 6 hours post-dose shows new onset second degree or higher AV block
- The ECG 6 hours post-dose shows a prolonged QTcF interval (>450 msec males, >470 msec females).

Should post-dose symptomatic bradycardia occur, the treating neurologist should be notified and he or she should initiate appropriate management, begin continuous ECG monitoring, and continue observation until the symptoms have resolved.

Should a patient require pharmacologic intervention for symptomatic bradycardia, continuous overnight ECG monitoring in a medical facility should be instituted, and the first dose monitoring strategy should be repeated the following day (Day 2). The first dose monitoring strategy should also be repeated at Day 5 if any cardiac safety issues were observed on Day 1.

Patients should have written instruction on when to return to clinic and a 24-hour contact phone number to call in the event of any new or warranted symptoms (e.g., chest pain, dizziness, palpitations, syncope, nausea, vomiting). Patients should be instructed not to drive on the same day after the first dose of study drug administration.

First dose monitoring procedures will also be followed at the Week 24 visit in Part A for patients who elect to continue in the blinded extension study, or for any patient who resumes treatment after missing more than 7 consecutive doses.

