10.2.3. Day 8 Visit

This visit will be performed for safety purposes. Patients will be instructed that they must take the Day 8 study drug dose at the clinic before 12:00 pm (noon), after the Holter monitor has been placed. Continuous Holter monitoring will be performed for 15 minutes predose and for 24 hours following dose administration for the first 75 randomized patients.

If clinically significant cardiac conduction abnormalities are not observed in the first 75 patients that are treated, Day 8 monitoring will be discontinued for the remaining patients enrolled in the study. The first-dose monitoring strategy should be repeated at Day 8 if any cardiac safety issues were observed at Day 5. See the monitoring guidelines in [Section 10.2.1.1](#) for further details.

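### The rule for ending Day 5 and Day 8 cardiac monitoring in Part A has two wordings, and the visit sections leave out heart rate (minor)

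*Protocol*

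**What the plan says.** The protocol states the conditional rule five times.

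Three statements name both kinds of finding:
- Synopsis, safety endpoints for Part A: "If clinically significant heart rate reductions or cardiac conduction abnormalities are not observed in the first 75 patients that are treated"
- Section 8.2.2: "If clinically significant heart rate reduction or cardiac conduction abnormalities are not observed"
- Section 9.1.1, Table 1 footnote 1: "If clinically significant heart rate reductions or cardiac conduction abnormalities are not observed"

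Two statements name conduction findings only:
- Section 10.2.2 (Day 5 visit): "If clinically significant cardiac conduction abnormalities are not observed in the first 75 patients that are treated, Day 5 monitoring will be discontinued"
- Section 10.2.3 (Day 8 visit): "If clinically significant cardiac conduction abnormalities are not observed in the first 75 patients that are treated, Day 8 monitoring will be discontinued"

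All five are current Version 4.0 text, and no order of precedence is given. Table 5 footnote 1, Section 11.2.1 and SAP Section 10.3 also limit Day 5 and Day 8 procedures to the first 75 patients. They give the base schedule without a condition, so they are not part of this inconsistency.

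**The concern.** This is an operative safety rule: someone has to look at the first 75 patients and decide whether routine monitoring at the two titration steps goes on. A reader working from the visit sections could end it despite clinically significant heart rate falls. A reader working from the Synopsis, Section 8.2.2 or Table 1 would find that the condition for stopping had not been met.

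The omitted finding matters to the design. Section 12.4 describes heart rate reduction as an expected effect of this drug class, and Section 9.2 gives limiting it as the reason for titrating. The Day 5 procedures in Section 10.2.2 include hourly vital signs, yet the rule in that same section, read literally, gives heart rate no role in the decision.

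What would be lost is a routine check at the dose step for patients whose Day 1 was clean.

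**Working it through.** There is no planned figure to reproduce. The check is whether the two wordings can lead to different actions and, if so, for whom.

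**Does the shorter wording cover heart rate?** The protocol's usage is mixed.
- Separate terms: the extended-monitoring criteria in Section 10.2.1.1 have one trigger for rate ("The heart rate 6 hours post-dose is < 45 bpm") and another for conduction ("The ECG 6 hours post-dose shows new onset second degree or higher AV block"). Section 9.1.2.5 also lists bradycardia alongside conduction abnormalities. Section 7.2.4 reports "Four subjects had Grade 2 cardiac-related AEs of bradycardia and/or conduction abnormality".
- Inclusive usage: elsewhere in Section 7.2.4, and in Section 7.3, bradycardia is described as one of the conduction abnormalities.

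So the shorter wording does not clearly cover heart rate. A drafting slip is plausible.

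**When do the decisions differ?** Taking the terms as separate, the outcomes in the first 75 patients are:

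| Significant heart rate fall | Significant conduction abnormality | Synopsis, 8.2.2, Table 1 | 10.2.2, 10.2.3 |
|---|---|---|---|
| No | No | Stop | Stop |
| No | Yes | Continue | Continue |
| Yes | Yes | Continue | Continue |
| Yes | No | Continue | **Stop** |

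One outcome in four differs. That is a count of cases, not a probability.

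**How many patients?** Inputs: about 210 patients randomized 1:1:1 in Part A, and a decision after the first 75.
- RPC1063 patients informing the decision: 75 × 2/3 = 50
- Later patients: 210 − 75 = 135
- Later patients on RPC1063, stepping from 0.25 to 0.5 mg at Day 5: 135 × 2/3 = 90
- Of these, stepping to 1 mg at Day 8: 135 / 3 = 45

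**How long until the next scheduled heart rate and ECG?** That is Day 29 ± 3 days (Section 10.2.4).
- After the Day 5 step: 29 − 5 = 24 days (21 to 27)
- After the Day 8 step: 29 − 8 = 21 days (18 to 24)

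The same gap arises whenever monitoring is properly stopped. It counts here only because the visit sections could stop monitoring when the other texts would not.

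**How likely is the differing case?** Section 7.2.4 describes four Phase 1 subjects with cardiac adverse events: one with AV block, two with sinus arrest and one with sinus bradycardia (1 + 2 + 1 = 4). The only one described with a rate finding alone was dosed at 3 mg, three times the top dose here. The Phase 1 titration data, on a different schedule, showed almost no further mean fall after Day 4, although a mean does not exclude falls in individuals. The documents give no rate of clinically significant falls at Day 5 or Day 8. The case is possible but probably uncommon.

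**The case against.** The strongest reply is that this is a copy-editing slip with little or no consequence.

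- **Continuation is inferred.** No text says in terms that patient 76 onward stays under monitoring, and several texts simply schedule it for the first 75. That is true, but a rule that ends monitoring if something is not observed has a purpose only if monitoring otherwise goes on.
- **Bradycardia may count as a conduction abnormality.** Sections 7.2.4 and 7.3 do use the inclusive phrasing, and on that reading little divergence remains. But Sections 9.1.2.5 and 10.2.1.1 separate the two, so the shorter wording is ambiguous at best.
- **The Day 8 loss is limited.** Table 5 and Section 10.2.3 schedule only a 24-hour Holter at Day 8, without the hourly vital signs and Hour 6 ECG done at Day 5. This stands. What goes at the 1 mg step is a heart rate recording, not six hours of observation.
- **Individual patients are protected either way.** All Part A patients are monitored on Day 1. Monitoring is repeated at Day 5 after a Day 1 issue and at Day 8 after a Day 5 issue. There is a 24-hour contact number, and the DMC reviews safety. This also stands, but the repeat rules need an earlier signal and so do not replace the check for a patient with a clean Day 1.
- **The decision may already have been taken.** The protocol version is dated 01 October 2014, and the Part A SAP, dated 20 May 2014, describes Day 5 and Day 8 data for the first 75 patients without condition. That suggests, but does not show, that the question was closed.

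**Conclusion.** The inconsistency holds: two wordings of one safety decision rule are in force, and no text ranks them. It is minor. The wordings part only if significant heart rate falls occur without significant conduction abnormalities in the first 75 patients, and the patient numbers above are ceilings rather than expected harm. They assume full enrolment of 210, exact 1:1:1 allocation and every later patient reaching the dose steps. Different decisions also depend on reading conduction abnormalities as not including heart rate, which the protocol supports in some places and blurs in others. Confidence is high that the wordings conflict. Whether the conflict affected any patient cannot be determined from the documents.

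**What to change.** In Sections 10.2.2 and 10.2.3, insert *heart rate reductions or* before the words on cardiac conduction abnormalities, so that both match the Synopsis, Section 8.2.2 and Table 1 footnote 1. Table 5 footnote 1 needs no change.

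If the 75-patient decision was made before Version 4.0, record which wording was applied. That record has further use, because Section 8.2.2 allows initial-dose monitoring in Part B to be changed in light of Part A safety results.

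The cost is four words in each of two sections. The possible downside is that Day 5 and Day 8 monitoring continues for more Part A patients if significant heart rate falls are seen, which the other three texts already imply. The practical gain is uncertain, since the documents do not say when the 75th patient was treated.

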10.2.3. Day 8 Visit

This visit will be performed for safety purposes. Patients will be instructed that they must take the Day 8 study drug dose at the clinic before 12:00 pm (noon), after the Holter monitor has been placed. Continuous Holter monitoring will be performed for 15 minutes predose and for 24 hours following dose administration for the first 75 randomized patients.

If clinically significant cardiac conduction abnormalities are not observed in the first 75 patients that are treated, Day 8 monitoring will be discontinued for the remaining patients enrolled in the study. The first-dose monitoring strategy should be repeated at Day 8 if any cardiac safety issues were observed at Day 5. See the monitoring guidelines in [Section 10.2.1.1](#) for further details.

10.2.4. Day 29 (Week 4 ± 3 days) Visit

The following assessments will be performed at the Week 4 visit:

- Blood/urine sampling for the following laboratory tests:
 - Hematology: RBC count, total and differential WBC count (basophils, eosinophils, lymphocytes, monocytes, and neutrophils), platelet count, hemoglobin, hematocrit, MCV, MCH, and MCHC.
Note: All total WBC and differential WBC counts will be blinded during the study.
 - Blood chemistry: sodium, potassium, chloride, calcium, magnesium, phosphate, blood urea nitrogen, random glucose, albumin, alkaline phosphatase, creatinine, SGPT/ALT, SGOT/AST, GGT, amylase, total bilirubin, conjugated bilirubin.
Abnormal laboratory parameters inconsistent with clinical presentation of MS or suspicious of underlying medical condition should be repeated for accuracy. If an increase of amylase above the clinically notable value (≥ 300 U/L) is observed at any post randomization visit, lipase should be tested to determine the origin of elevated amylase (pancreatic versus extra pancreatic).
 - Urine beta-hCG (females of childbearing potential only). If the urine pregnancy test is positive, do not dose and confirm with a serum pregnancy test.
 - Standard PK sampling: PK samples are to be taken 2 to 6 hours following administration
- Vital signs: body temperature, blood pressure and heart rate
- 12-lead ECG
- Dispense study drug and patient diary
- Review study drug accountability and compliance
- Suicidality assessment using the C-SSRS
- Record concomitant therapy

- Record AEs/SAEs

10.2.5. Day 57 (Week 8 ± 3 days) Visit

The following assessments will be performed at the Week 8 visit:

- Urine beta-hCG (females of childbearing potential only). If the urine pregnancy test is positive, do not dose and confirm with a serum pregnancy test.
- Vital signs: body temperature, blood pressure and heart rate
- Dispense study drug and patient diary
- Review study drug accountability and compliance
- Brain MRI
- Suicidality assessment using the C-SSRS
- Record concomitant therapy
- Record AEs/SAEs

10.2.6. Day 85 (Week 12 ± 3 days) Visit

Note: Subjects are to be instructed not to take their dose of study drug at home, and will be administered study drug at the clinic after laboratory procedures have been completed. Subjects should arrive at the clinic in a fasted state.

The following assessments will be performed at the Week 12 visit:

- Blood/urine sampling for the following laboratory tests:
 - Hematology: RBC count, total and differential WBC count (basophils, eosinophils, lymphocytes, monocytes, and neutrophils), platelet count, hemoglobin, hematocrit, MCV, MCH, and MCHC
Note: All total WBC and differential WBC counts will be blinded during the study.
 - Blood chemistry: sodium, potassium, chloride, calcium, magnesium, phosphate, blood urea nitrogen, random glucose, albumin, alkaline phosphatase, creatinine, SGPT/ALT, SGOT/AST, GGT, amylase, total bilirubin, conjugated bilirubin.
Abnormal laboratory parameters inconsistent with clinical presentation of MS or suspicious of underlying medical condition should be repeated for accuracy. If an increase of amylase above the clinically notable value (≥ 300 U/L) is observed at any post randomization visit, lipase should be tested to determine the origin of elevated amylase (pancreatic versus extra pancreatic)
 - Urine beta-hCG (females of childbearing potential only). If the urine pregnancy test is positive, do not dose and confirm with a serum pregnancy test.
 - Standard PK sampling: PK sample is to be taken prior to dose administration
- Administer study drug
- Vital signs: body temperature, blood pressure and heart rate

CONFIDENTIAL

The information contained herein may not be used, disclosed, or published without the written consent of Receptos.

- 12-lead ECG
- Dispense study drug and patient diary
- Review study drug accountability and compliance
- Brain MRI
- EDSS and neurological examination
- MSFC AND LCLA
- Pulmonary function tests including FEV₁ and FVC measurements
- Suicidality assessment using the C-SSRS
- Record concomitant therapy
- Record AEs/SAEs

10.2.7. Day 113 (Week 16 ± 3 days) Visit and Day 141 (Week 20) Visit

The same assessments will be performed at the Week 16 visit and the Week 20 visit, as follows:

- Urine beta-hCG (females of childbearing potential only). If the urine pregnancy test is positive, do not dose and confirm with a serum pregnancy test.
- Vital signs: body temperature, blood pressure and heart rate
- Dispense study drug and patient diary
- Review study drug accountability and compliance
- Brain MRI
- Suicidality assessment using the C-SSRS
- Record concomitant therapy
- Record AEs/SAEs

